4.4.3. ARIA-H incidence and severity of ARIA events

ARIA-H includes microhemorrhage and superficial siderosis. Total number of participants with microhemorrhage, superficial siderosis, as well as overall ARIA-H events will be reported at Week 24 and Week 52 by treatment arm. Incidence proportion of microhemorrhage, superficial siderosis, and overall ARIA-H per arm will be estimated from both time points. A posterior distribution of relative risk reduction in ARIA-H between one alternative dosing regimen and the standard dosing regimen by Week 24 or by Week 52 will be derived through a Bayesian logistic regression using 24-week or 52-week ARIA-H data coupled with priors constructed in a similar way as mentioned in Section 4.3.2 or Section 4.4.1. Then a posterior probability of at least 20% relative risk reduction in ARIA-H in 24 weeks or 52 weeks comparing one alternative treatment

arm versus the standard arm will be calculated. Sensitivity analyses will be similar to approaches as mentioned in Section 4.3.3.

For outputs including radiographic severity, below table contains the definitions used for 3-point ARIA-E and ARIA-H categorizations. A 5-point ARIA-E categorization has mild+ and moderate+ levels besides mild, moderate, and severe levels defined by the 3-point ARIA-E categorizations. Among participants with at least 1 ARIA-E or ARIA-H event during the study, number and percentage of participants with their maximum radiographic severity value in the categories of mild, moderate, and severe will be presented by treatment arm from 24-week and 52-week ARIA data when a 3-point rating of ARIA severity is used. Among participants with at least 1 ARIA-E event during the study, number and percentage of participants with their maximum radiographic severity value using the 5-point severity scale will be reported by treatment arm for both times points as well. At Week 24 and Week 52, Fisher's exact tests will be applied to determine if severe ARIA-E or ARIA-H events are distributed evenly while comparing the dosing skip regimen vs. standard dosing regimen, the titration regimen vs. standard dosing regimen.

An additional approach to Fisher's exact test will be used to investigate the association between treatment arm and ARIA (-E or -H) severity with a Cochran-Mantel-Haenszel (CMH) test. Fisher's exact test treats severity as a nominal variable whereas CMH can handle severity as an ordinal variable.

Table 4.1. Radiographic severity of ARIA-E and ARIA-H.

ARIA Type	Radiographic Severity	Definition
ARIA-E	Mild	FLAIR hyperintensity confined to sulcus and/or cortex/subcortex white matter in one location <5 cm.
	Mild+	Mild presentation in more than one site of involvement
	Moderate	FLAIR hyperintensity 5 to 10 cm in single greatest dimension, or more than 1 site of involvement, each measuring < 10 cm.
	Moderate+	Moderate involvement (area of FLAIR hyperintensity measuring 5-10 cm in single greatest dimensions) in more than one site of involvement, each measuring less than 10 cm in a single greatest dimension.
	Severe	FLAIR hypersensitivity > 10 cm with associated gyral swelling and sulcal effacement. One or more separate/independent sites of involvement may be noted.

ARIA-H microhemorrhage	Mild	≤ 4 treatment-emergent total microhemorrhages and new incident microhemorrhages
	Moderate	5-9 treatment-emergent total microhemorrhages or new incident microhemorrhages, whichever is greater
	Severe	≥ 10 treatment-emergent total microhemorrhages or new incident microhemorrhages, whichever is greater
ARIA-H superficial siderosis	Mild	1 new or increased focal area of superficial siderosis
	Moderate	2 new or increased focal areas of superficial siderosis
	Severe	> 2 new or increased focal areas of superficial siderosis

Abbreviations: ARIA-E = amyloid-related imaging abnormalities- edema/effusions; ARIA-H = amyloid-related imaging abnormalities- hemorrhage/hemosiderin deposition; FLAIR = fluid attenuated inversion recovery.

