# 9.3. Statistical Analyses

# 9.3.1. General Considerations

Statistical analysis of this study will be the responsibility of the Sponsor or its designee.

All analyses related to safety, including analyses for the primary endpoint, will be based on the Safety Analysis Set.

The analysis for the secondary objective related to amyloid plaque deposition will be based on the Safety Analysis Set unless otherwise specified in the SAP.

To allow for evaluation of the primary and secondary hypotheses at 24, 52, and 76 weeks, the assessments of corresponding primary and secondary objectives are expected to occur after all participants in the Safety Analysis Set have had the opportunity to complete visits 12, 19, and 25, respectively, including PET and MRI assessments. Data collected during the immunogenicity and safety follow-up period will be summarized and analyzed separately.

For analyses using historical data, the sources of historical data and analysis considerations will be described in the SAP.

When change from baseline is assessed, participants will be included in the analysis only if both a baseline and a postbaseline measure are available. Unless otherwise defined, a baseline measure is the last non-missing observation collected prior to the first administration of study medications.

Any change to the data analysis methods described in the protocol will require an amendment only if it changes a principal feature of the protocol. Any other change to the data analysis methods described in the protocol, and the justification for making the change, will be described in the SAP and the CSR. Additional exploratory analyses of the data will be conducted as deemed appropriate.

Handling of missing, unused, and spurious data are addressed prospectively in the overall statistical methods described in the protocol and in the SAP, where appropriate. Any adjustments to the planned analyses will be described in the final CSR.

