2.1. Multiplicity Adjustment

Adjustments for multiplicity will not be applicable for this study.

3. Analysis Sets

For the purposes of analysis, the following analysis sets are defined below:

Participant Analysis Set	Description
Entered	All participants who sign the informed consent form.
Randomized	All participants who are randomly assigned to 1 of 4 treatment arms.
Safety analysis set	All randomized participants who are exposed to at least 1 dose of donanemab. This safety analysis set is used to analyze all the safety endpoints during the treatment period plus safety follow-up.
Evaluable efficacy analysis set	Randomized participants with baseline and at least 1 post-baseline measure of interest.
Per-Protocol analysis set	All subjects in the Randomized Analysis Set population who also:
	 signed the inform consent form had no violations of inclusion/exclusion criteria
	 had no study dosing algorithm violation (such as if subjects randomized to treatment A were given treatment B or subjects randomized to treatment A never received the assigned study drug) adhered to the dosing titration scheme required in the first 16 weeks of this study
	were not considered non-compliant with regard to study drug

4. Statistical Analyses

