4.1. General Considerations

As 4 donanemab dosing regimens including the standard one are available for Study AACQ, any safety or biomarker analysis will involve 3 comparisons: 1) dose skipping vs. standard dosing; 2) titration vs. standard dosing; 3) Cmax (concentration maximum) vs. standard dosing.

Safety analyses will include subjects who are randomized to study treatment and who take at least 1 dose of treatment. Subjects will be analyzed according to the treatment arm to which they were assigned.

Unless otherwise specified, analyses for ARIA events are based on MRI findings or AE (adverse events) reporting. ARIA safety analyses will cover both ARIA-E and ARIA-H events by Week 24 as well as by Week 52. Bayesian logistic regression method is proposed to obtain a posterior distribution regarding relative risk reduction in ARIA-E or ARIA-H at Week 24 or 52 for each of 3 comparisons mentioned above. The details of logistic regression model, prior elicitation, and computation for the posterior distribution will be presented in Section 4.3.2. From each derived posterior distribution of RD_{21} , RD_{31} , and RD_{41} , summary statistics will be reported which include posterior mean, posterior median, posterior mode, a 2-sided equal-tailed 95% posterior interval (often cited as credible interval in Bayesian literature), and a posterior probability of achieving a minimum of 20% relative risk reduction in ARIA-E.

Frequentist methods will be used for the rest of the study objectives. All frequentist tests will be conducted at a 2-sided alpha level of 0.05; 2-sided confidence intervals (CIs) will be displayed with a 95% confidence level.

Unless otherwise noted baseline is defined as the last measurement prior to dosing. When change from baseline is assessed, subjects will only contribute to the analysis if both a baseline and a post-baseline measurement are available. Endpoint is the last non-missing post-baseline measurement within the time period for the given analysis.

To allow for evaluation of the primary and secondary hypotheses at 24 and 52 weeks, database locks and the assessments of corresponding primary and secondary objectives are expected to occur after all participants in the Safety Analysis Set have had the opportunity to complete visits 12 and 19 including PET and MRI assessments. The sponsor may choose not to have a separate database lock after visit 19 and wait to perform the analyses for 52-week data until the final database lock.

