Only participants with at least 1 occurrence of ARIA-E will be included for analyses to correlate severity of ARIA-E with change of NfL scores from baseline. For instance, to correlate severity of ARIA-E at Week 24, a proportional odds model will be used. Such a model will include treatment arm, APOE e4 genotype status, number of microhemorrhages at baseline, baseline presence of superficial siderosis, baseline amyloid centiloid, mean arterial pressure, antihypertensives, and percent change of NfL from baseline in 24 weeks.

The association between other plasma-based biomarkers, like pTau, A β levels (40 and 42), GFAP, sTREM2, or hsCRP and the frequency and severity of ARIA-E will follow the same analysis plan outlined above.

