The Bayesian power calculation was performed through simulations in both data generation and model fitting steps. In the data simulation stage, 1000 ARIA-E data sets were generated for every treatment arm. It was assumed that ARIA-E rate by Week 24 in the standard dosing regimen was 18.5% based on observations from AACI Addendum 9 data. In each alternative dosing regimen, ARIA-E rate was set to be equal to 11.1%, which translates to 40% relative risk reduction in ARIA-E compared to standard dosing regimen.

In the model fitting stage, a normal prior, N(0,4) was assigned to individual slope parameter of Arm 2, 3, and 4, respectively in the Bayesian logistic regression model. The intercept parameter was given a normal mixture prior, $0.5 \times N(-1.48, 4) + 0.5 \times N(-1.48, 30.19)$. The component prior mean (-1.48) in the mixture prior is equal to the natural log odds ratio of ARIA-E rate at 18.5% observed from historical study. For any simulated ARIA-E data with a complete sample size of 720, posterior samplers of RD_{21} , RD_{31} , and RD_{41} were simulated from 3 Markov chains with each chain composed of 10000 iterations after 10000 burn-ins. Among 1000 datasets generated, 927 satisfied at least one of the following probability statements:

```
Pr(RD_{21} \ge 0.2 \mid \text{simulated 24-week ARIA-E data}) > 0.8;

Pr(RD_{31} \ge 0.2 \mid \text{simulated 24-week ARIA-E data}) > 0.8;

Pr(RD_{41} \ge 0.2 \mid \text{simulated 24-week ARIA-E data}) > 0.8.
```

Hence, the reported power was 92.7% based on simulations.

In the null scenario where all the dosing regimens have the same true ARIA-E rate of 18.5% by Week 24, the false positive rate was controlled at 5% one-sided, or equivalently 10% two-sided.

The power and false-positive rate of the study were determined by simulations using R 4.1.2. Particularly, posterior samplers were generated through rjags package in R.

6. Supporting Documentation

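### SAP 4.4.3 gives ARIA severity percentages among ARIA cases, leaves the denominator of the severity tests open, and plans no severe-ARIA proportion or difference over all treated participants

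*SAP*

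**What the plan says.** ARIA-E and ARIA-H by severity is a secondary endpoint in Protocol Section 3 and SAP 1.1. SAP 4.4.3 tabulates it as "Among participants with at least 1 ARIA-E or ARIA-H event during the study, number and percentage of participants with their maximum radiographic severity value" on the 3-point scale, by arm, from Week 24 and Week 52 data. A 5-point table for ARIA-E has the same restriction to cases.

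The tests come next: "Fisher's exact tests will be applied to determine if severe ARIA-E or ARIA-H events are distributed evenly". A CMH test is added because "Fisher's exact test treats severity as a nominal variable whereas CMH can handle severity as an ordinal variable". Neither sentence names a denominator, and the severity definitions in Table 4.1 of that section have no level for no ARIA.

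A general default exists. SAP Section 3 says of the safety set: "This safety analysis set is used to analyze all the safety endpoints during the treatment period plus safety follow-up". SAP 4.1 adds: "Safety analyses will include subjects who are randomized to study treatment and who take at least 1 dose of treatment". Protocol 9.3.1 agrees: "All analyses related to safety, including analyses for the primary endpoint, will be based on the Safety Analysis Set". Where the SAP wants a case-only analysis elsewhere, it says so, as in 4.5.2: "Only participants with at least 1 occurrence of ARIA-E will be included for analyses to correlate severity of ARIA-E with change of NfL scores".

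SAP 4.6.6 plans other relevant outputs by arm: a severity shift table by visit, ARIA-E split into symptomatic and asymptomatic, and the proportion with serious ARIA. It also plans a per-protocol version of the ARIA incidence overview. The per-protocol set in SAP Section 3 requires adherence to the titration scheme over the first 16 weeks. Protocol 6.6, 7.1 and 7.1.2 allow a dose increase to be withheld, or dosing to be interrupted or stopped, because of ARIA.

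**The concern.** Having ARIA is a post-randomisation outcome, and lowering its frequency is the purpose of the alternative regimens. If a regimen succeeds, its cases are fewer and may differ in kind from those in the standard arm. The severe share among cases then mixes two effects: how many participants get ARIA at all, and how severe it is when it occurs. The question for a treated participant is the risk of severe ARIA. That needs everyone treated in the denominator, and 4.4.3 plans no such proportion or between-arm difference.

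The test wording adds to this. The general default points to all treated participants, while the sentences immediately before the tests are restricted to cases. Two programmers could follow the text faithfully and run different tests on a listed secondary endpoint.

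The per-protocol overview raises a smaller issue of the same kind. If an ARIA-driven dosing change counts as non-adherence, an analysis of ARIA incidence removes participants because they had ARIA.

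**Working it through.** **Inputs from the documents (SAP 4.1 and Section 5).** ARIA-E by Week 24 is 18.5% in the standard arm. For each alternative, "ARIA-E rate was set to be equal to 11.1%, which translates to 40% relative risk reduction in ARIA-E". 800 participants are randomised 1:1:1:1, so 200 per arm, or 180 after the assumed 10% loss. Frequentist tests are two-sided at 5%. Section 4.4.3 states no figure of its own to reproduce. The documents give no severity mix.

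**Step 1, the plan's rates.** 0.185 × 0.60 = 0.111, as stated. Expected ARIA-E cases are 200 × 0.185 = 37 and 200 × 0.111 = 22.2. At 180 per arm they are 33.3 and 20.0.

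**Step 2, what a case-only ratio shows.** Let s be the severe share among standard-arm cases and R the true risk ratio for severe ARIA-E in all treated participants.
- Severe share among alternative-arm cases = R × s × 0.185 / 0.111.
- Divided by s, the case-only ratio = R / 0.60. The share s cancels.

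| True severe RR | Case-only ratio |
|---|---|
| 0.60 | 1.00 |
| 0.80 | 1.33 |
| 1.00 | 1.67 |

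This step needs only the plan's own rates.

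**Step 3, how often a test would mislead.** This needs an assumed s; 10%, 15% and 25% are used. Take 200 per arm, total ARIA-E falling from 18.5% to 11.1%, and severe risk unchanged. At s = 15%, the severe risk is 0.15 × 18.5% = 2.8% in both arms, but the severe share among cases is 15% against 25%.

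| Test | s = 10% | s = 15% | s = 25% |
|---|---|---|---|
| Case-only Fisher signals worse severity | 8.6% | 12.4% | 22.2% |
| All-participant Fisher rejects, either direction | 1.6% | 2.2% | 2.8% |

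A case-only ordinal test signals worse severity in 7.9%, 11.4% and 20.4% of simulated trials (mild/moderate/severe mixes of 40/50/10, 35/50/15 and 30/45/25%). If the whole reduction is in mild cases (60/30/10% mix), the figure is 42.9%, so the size depends strongly on the assumed mix.

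**Step 4, should the ordinal test also move to all participants?** With no ARIA as the lowest level and severe risk unchanged, it favours the alternative in 33-41% of trials, because incidence drives it. When incidence is equal and only severity shifts (35/50/15% to 60/33/7%), its power is 56% among cases and about 13% in all participants. The ordinal test is therefore better kept among cases, as description.

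**Step 5, precision of the all-participant comparison.** For a true 40% cut in severe ARIA-E, Fisher power at 200 per arm is 2.8%, 5.4% and 10.2% for s = 10%, 15% and 25%. At s = 15% the expected severe counts are 5.55 and 3.33 of 200. The risk difference is -1.1 points, with Newcombe 95% CI about -4.6 to 2.2.

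**Step 6, per-protocol overview.** If a share q of ARIA-E cases is excluded, the rate becomes p(1 - q) / (1 - pq). The values of q are assumptions.
- Equal q = 0.2: 18.5% becomes 15.4%, and the RR moves from 0.60 to 0.59.
- Equal q = 0.7: 18.5% becomes 6.4%, and the RR moves to 0.57.
- Unequal q, 0.2 standard and 0.3 alternative: RR 0.52. Reversed: RR 0.66.

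**The case against.** The strongest reply is that little is lost. Section 4.4.3 gives numbers as well as percentages, so the severe risk per treated participant is one division away. SAP 4.6.6 adds the shift table and the symptomatic and serious ARIA outputs by arm. The Safety Analysis Set default, together with the explicit case-only limit in 4.5.2, favours the all-participant reading of the Fisher sentence. The severity distribution among cases is a legitimate description. The misleading-signal rates need the case-only reading, an assumed severity mix and a regimen that prevents only non-severe ARIA-E. The proposed comparison has low power.

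Most of this stands and limits the point. A reader might infer that the plan hides severe risk, or that the tests are definitely case-only. The documents support neither. What remains is that the default set says who is eligible, not whether ARIA-free participants enter a severity test, and that no all-participant severe proportion or difference is planned. The Step 2 distortion needs no assumed mix.

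On the per-protocol set, the stated reason in the SAP version history is robustness to protocol deviations, and a permitted ARIA-driven change need not be a deviation. The details of withholding an increase are deferred to the Manual of Operations, which is not among the documents. Exclusion because of ARIA is therefore a possibility under a literal reading, not a certainty.

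**Conclusion.** The point holds as a limited analysis issue that is worth correcting. The severity percentages in 4.4.3 are not randomised comparisons, and the test denominator is unstated. At the plan's rates, the case-only severe ratio is the true ratio divided by 0.60. That result rests only on 18.5% and 11.1%; the 8.6-22.2% Fisher signal rates rest also on an assumed 10-25% severe share, unchanged severe risk and the case-only reading.

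It should not be read as a threat to the trial's conclusion. No decision rule uses these tests, and the primary analysis follows a treatment-policy strategy. The per-protocol matter is minor: it touches one sensitivity overview, leaves the RR at 0.59-0.57 under equal exclusion, and moves it more only if exclusion differs between arms, which the documents do not establish.

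**What to change.** In SAP 4.4.3, at Weeks 24 and 52:
- Report the proportion with severe ARIA-E and with severe ARIA-H among all Safety Analysis Set participants by assigned arm, with the risk difference and 95% CI for each alternative regimen against standard.
- State that the Fisher test of severe events uses that denominator.
- Keep the among-cases tables and the ordinal CMH test as descriptive, labelled as non-randomised comparisons.

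Separately, state in SAP Section 3 that, for per-protocol ARIA analyses, a protocol-permitted dosing change made because of ARIA is not counted as non-adherence. This matches the stated purpose and changes no dosing rule.

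The cost is wording plus one table row with a difference and interval per comparison; no new data are needed. The drawback is the low power shown in Step 5, so the interval, not the p-value, is what should be read.

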4.4.4. PK/PD analysis

PK/PD analyses will be covered in a separate PK/PD statistical analysis plan.

4.4.5. Immunogenicity

The frequency and percentage of subjects with preexisting (baseline) ADA, ADA at any time after baseline, and TE-ADAs to donanemab will be summarized by treatment arm. If no ADAs are detected at baseline, TE-ADAs are defined as those with a titer 2-fold (1 dilution) greater than the MRD of the assay. For samples with ADA detected at baseline, TE-ADA are defined as those with a 4-fold (2 dilutions) increase in titer compared to baseline. For the TE-ADA subjects, the distribution of maximum titers will be summarized. The frequency of subjects with neutralizing antibodies (subset of the TE-ADA patients) will also be summarized. If the number of subjects experiencing TE-ADA is sufficiently high, further exploratory analyses will be performed to characterize their impact on exposure and clinical outcomes.

4.5. Tertiary/Exploratory Endpoints Analysis

4.5.1. Exploratory MRI sequences

The table below lists exploratory MRI sequences, and pre-specified endpoints for exploratory analyses, as well as scheduled visits for exploratory endpoints. Unscheduled MRIs will be

included for analyses of exploratory endpoints. Information about four dosing regimens will be combined before performing any analysis here.

Table 4.2. Prespecified endpoints for exploratory MRI sequences.

MRI Sequences	Scheduled Visit	Endpoints
3D FLAIR	2, 4, 8, 12, 19	 ARIA-E presence ARIA-E severity White matter disease burden
3D T2	2, 4, 8, 12, 19	PVS (perivascular spaces) score in centrum semi ovale
SWI	2, 4, 8, 12, 19	 Number of new and total ARIA-H microhemorrhages Number of total ARIA-H superficial siderosis
DTI	2, 4, 8, 12, 19	 Whole cortex MD (mean diffusivity), and FW (free water fraction) Hippocampal MD and FW Whole white matter FA (fractional anisotropy)
fMRI	2	Peak activation in occipital cortex (top 200 voxels based on z-scored activation maps)
vMRI	2, 4, 8, 12, 19	 Hippocampal volume, cortical volume, ventricle volume, whole brain volume (all normalized for intracranial volume) Cortical thickness
FLAIR 3D, 3DT2, SWI	2	Vascular risk score for CAA based on Boston 2.0 Criteria

Abbreviations: ARIA = amyloid-related imaging abnormalities; CAA = cerebral amyloid angiopathy; DTI = diffusion tensor imaging; FLAIR = fluid attenuated inversion recovery; FW = free water fraction; fMRI = functional magnet resonance imaging; MD = mean diffusivity; PVS = perivascular spaces; SWI = susceptibility weighted imaging; vMRI = volumetric magnet resonance imaging.

Prediction of ARIA

Logistic regression analyses will be used to assess four types of baseline models to predict ARIA-E incidence at Week 24:

1) The model will include baseline risk factors of ARIA-E: APOE e4 genotype, number of microhemorrhages at baseline (determined by standard safety sequences), presence of superficial siderosis at baseline (determined by standard safety sequences), amyloid centiloid at baseline, mean arterial pressure, and anti-hypertensives.

- 2) The model will include all baseline exploratory MRI endpoints discussed before. The following markers will also be considered for inclusion to the model: white matter disease burden from 3D FLAIR, number of microhemorrhages at baseline form SWI, cortical superficial siderosis from SWI, PVS in centrum semi ovale, whole cortex MD, whole cortex FW, hippocampal MD and FW, whole white matter FA, fMRI peak activation in occipital cortex, hippocampal volume, cortical volume, ventricle volume, whole brain volume, cortical thickness, and CAA.
- 3) Exploratory MRI endpoints listed above will be added individually to the baseline ARIA-E risk model described in 1.
- 4) The model will include all baseline risk factors described in 1) and all exploratory endpoints described in 2).

AIC (Akaike information criteria) as well as BIC (Bayesian information criteria) statistics will be generated for each proposed model above. While both the AIC and BIC will be generated, the BIC will be used to evaluate the model. In the case of SWI endpoints, the counts of microhemorrhages and superficial siderosis will come from baseline SWI instead of its standard safety MRI equivalent. In the case of 3D FLAIR, white matter burden score will come from 3D FLAIR instead of the standard safety sequence MRI equivalent. An ROC curve (receiver operating characteristic curve) can be plotted from individual ARIA-E risk prediction model and AUC (area under the curve) will be computed to tell how each model is capable of distinguishing between ARIA-E subjects and ARIA-E free subjects. A possible AUC value is between 0.5 and 1, and the larger the AUC, the better the discriminatory ability.

Comparison between standard and exploratory MRI sequences

To assess the agreement of exploratory versus standard MRI sequences at baseline, a contingency table assessing agreement on white matter disease burden, number of microhemorrhages, and presence of cortical superficial siderosis will be evaluated separately using a Bowker's test of symmetry.

For scans with both SWI and T2*-GRE data, Spearman's rank correlations between the number of microhemorrhages identified by SWI and that identified by T2*-GRE will be provided for baseline scans and all scans. For scans with both 3D FLAIR and 2D FLAIR data in which ARIA-E was detected in either 3D FLAIR or 2D FLAIR, a Spearman's rank correlation will be computed from the severity of ARIA-E assessed by 3D FLAIR versus that assessed by 2D FLAIR (severity will be assigned to zero if there is no presence of ARIA-E).

To assess the agreement of exploratory versus standard MRI sequences in monitoring ARIA, a contingency table assessing agreement on maximum severity, will be constructed for ARIA-E and ARIA-H separately using a Bowker's test of symmetry.

To compare temporal dynamics between exploratory versus standard MRI sequences, mean and standard deviation of number of days to 1st ARIA event will be reported for 2D FLAIR versus 3D FLAIR (ARIA-E) and for GRE (gradient recalled echo) versus SWI (ARIA-H). Percentage of exploratory scans still showing ARIA-E or ARIA-H when standard scan said ARIA-E or ARIA-H was resolved.

